12.1 Statistical Power

The proposed study is a pilot investigation intended to gather preliminary data on the safety and efficacy of marijuana in people with chronic, treatment-resistant PTSD. Because of their exploratory nature, pilot studies are often not powered for detecting the desired effect. Because it is a pilot study in a small sample, results will be used to assess variability of the outcome measures as inputs for calculation of sample sizes for adequately powered subsequent studies. This study will be the first to examine the effects of marijuana on PTSD.

This pilot RCT is the first study of its kind intended to gather estimates of effect size of marijuana for PTSD. In the absence of published effect sizes of marijuana for PTSD, possible effect sizes are estimated to be 0.4 (small to medium effect) for a between-subject comparison to ensure an adequately powered study size, based on a recent meta-analysis conducted with the National Center for PTSD [172]. Thus in the proposed study, $N=76$ with 19 participants randomized to each group will have 82% power to detect these or greater differences between groups on the same primary outcome measure (change in CAPS-5 total score) used to obtain FDA approval for PTSD medications. Similar calculations would apply for secondary analyses.

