4.2 Randomization and Participant Numbering

To achieve sufficient statistical power and account for dropouts, about 116 participants will be stratified by site and randomized in a 1:1:1:1 ratio across the four treatment groups (High THC, High CBD, THC/CBD, or Placebo) based on a sequential order of enrollment into the study. Participants will be assigned a randomization code that will correspond to a blinded condition assignment. Randomization and enrollment will halt when 76 participants complete Stage 1 (at least N=19 per group). In order to maintain the blind for participants, site staff, IRs, and sponsor staff, a central electronic database will be utilized for randomization based on validated computer-generated lists. The Stage 1 randomization list will utilize blocks to balance treatment assignments. Stage 2 randomization will utilize multiple validated randomization lists that re-randomize participants in a blinded manner to one of two new treatment assignments in a 1:1 ratio, excluding the previously assigned Stage 1 dose and the placebo condition as possibilities.

The blind may be broken for an individual participant if there is an AE or other emergency requiring knowledge of the participant's marijuana condition assignment. This emergency unblinding would require approval from the site CI and Coordinating Investigator. For this purpose, the Randomization Monitor will provide dose assignment through the electronic randomization system. In all other cases, the blind will be maintained until all participants have completed the study and the database is locked. The Coordinating Investigator, Co-investigator, CIs, IR, and participant will be blind to condition assignment.

Prior to enrollment, participants at Site 01 will be tracked with a screening number assigned sequentially starting at "S1001," and participants at Site 02 will be tracked with a screening number assigned sequentially starting at "S2001." Participants who meet eligibility criteria will be enrolled in the study and assigned a five-digit participant number. The first two digits will be "01 or 02" and will identify the study site. The next three digits identify the participant within the site and will be assigned sequentially, with 101 corresponding to the first participant enrolled, e.g. the first participant enrolled at site 01 will be 01101, second 01102, and the first participant enrolled at Site 02 will be 02101, second 02102, etc.

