12.0 Data Analysis

Key Personnel, MAPS, and the biostatistician will agree on a detailed Statistical Analysis Plan prior to the beginning of recruitment. The biostatistician will perform an "intent to treat" (ITT) analysis using repeated measures analysis of covariance (ANCOVA) to compare demographics. Distribution of treatment dropouts will be examined by condition and if found to be unequal, the sponsor will control for group assignment in the ITT analysis.

Primary analysis of observer-blind CAPS-5 data collected at Baseline and end of Stage 1 will be conducted using ANCOVA with marijuana concentration as a between-subject factor and time of assessment as a within-group factor. If effects of marijuana concentration are detected at Stage 1, a similar secondary analysis will also be performed with Stage 2 data using Stage 1 data as a covariate for each outcome measure. Effect size will be estimated based on all outcome measures using Cohen's techniques. The biostatistician will conduct secondary exploratory analyses of weekly assessments of PCL-5, ISI, IDAS, IPF, WBR, CSSRS, MWC, CUDIT-R, DEQ and ACT scores using repeated measures ANCOVA or generalized linear mixed modeling, as described in the Statistical Analysis Plan. Statistical significance ($p < .05$) will be determined for all tests. All available data from repeated outcome assessments of all participants who are randomized, even if they withdraw from the allocated treatment prior to the primary endpoints, will be included in ITT analysis.

A repeated measures ANCOVA comparison of ratings on the DEQ and pulse will be conducted, with marijuana condition as the main factor in the analysis. If a main effect of marijuana concentration is observed then pairwise comparisons will be conducted to detect differences between each marijuana concentration.

Secondary exploratory analyses will be conducted examining weekly assessments of self-reported (via the ISI) and objective (via Actigraphy) measures of sleep. Independent repeated measures ANCOVAs will be conducted. In terms of self-reported sleep, weekly total scores from the ISI will be entered as the repeated measure with group entered as the IV. In terms of objective sleep (via Actigraphy) repeated measures ANCOVAs will be conducted with weekly total sleep time (TST), wake after sleep onset (WASO), sleep

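### Section 12.1 claims 82% power for an unlabelled effect size of 0.4; the figure needs a largest group difference in change of 0.8 to 1.1 SD, and a standardized mean difference of 0.4 has about 15–26% power

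*Protocol*

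**What the plan says.** Section 12.1 (Statistical Power) takes its effect size from a cited meta-analysis of PTSD treatments: "possible effect sizes are estimated to be 0.4 (small to medium effect) for a between-subject comparison to ensure an adequately powered study size". From this it concludes that N = 76, "with 19 participants randomized to each group will have 82% power to detect these or greater differences between groups", where the outcome is change in CAPS-5 total score. It then adds: "Similar calculations would apply for secondary analyses". Earlier in the same section there is a general caution that "pilot studies are often not powered for detecting the desired effect". The section gives no metric for the 0.4, no test, no SD and no baseline-to-endpoint correlation.

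Section 12.0 (Data Analysis) describes the primary analysis of CAPS-5 at Baseline and end of Stage 1 as "ANCOVA with marijuana concentration as a between-subject factor and time of assessment as a within-group factor", with significance at 0.05. Its intent-to-treat set is "All available data from repeated outcome assessments of all participants who are randomized".

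Section 4.2 relies on the power claim when it sets the recruitment target: "To achieve sufficient statistical power and account for dropouts, about 116 participants will be stratified by site". Enrolment stops when 76 participants, at least 19 per group, complete Stage 1.

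**The concern.** An effect size of 0.4 means different things in different metrics. As a standardized mean difference, 0.4 SD is between the usual small and medium benchmarks, which is how the protocol labels it. As Cohen's f for four groups, 0.4 is a large effect, because f is the standard deviation of the group means in SD units and the gap between the highest and lowest mean is at least twice that. The power figure appears to belong to the second metric and the label to the first.

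A reader who takes the section at its word would believe that Stage 1 is very likely to detect a small-to-medium benefit, and would count a null result as strong evidence against one. Section 4.2 rests the recruitment target on the same claim, and the last sentence of Section 12.1 carries it over to the secondary analyses.

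**Working it through.** **Inputs.** Four groups, 1:1:1:1 (Section 4.2); 19 per group, N = 76, outcome change in CAPS-5, effect size 0.4 (Section 12.1); alpha 0.05 and a group-by-time primary model (Section 12.0). The 19 per group are completers, so no further allowance for dropout is made. The correlation is not given and is varied below as an assumption.

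**1. Reproducing the 82%.** For an omnibus F test on change, the noncentrality is λ = f² × N with 3 and 72 degrees of freedom. With f = 0.40:

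λ = 0.16 × 76 = 12.16, power = 82.3%.

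A second route gives the same number. For the group-by-time interaction with m = 2 time points, λ = f² × N × m / (1 − ρ). With f = 0.2 and an assumed ρ = 0.5:

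λ = 0.04 × 76 × 2 / 0.5 = 12.16, power = 82.3%.

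This is the same alternative in other units. With two time points, group differences in change are twice the interaction deviations, and at ρ = 0.5 the SD of change, σ√(2(1 − ρ)), equals σ. So an interaction f of 0.2 is f = 0.4 on change. The second route depends on ρ: it gives 66.8% at ρ = 0.3 and 96.9% at ρ = 0.7. The protocol does not show which route was used.

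**2. What f = 0.40 means as a difference between groups.** If d is the largest difference between two group means in SDs of change, then f = c × d, where c depends on the pattern of the four means. The table gives the d needed for f = 0.40 (0.40 / c), then the f, the power and the group size when d = 0.4.

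| Pattern of means | c | d needed for f = 0.40 | f at d = 0.4 | Power, N = 76 | Power, N = 116 | n per group for 82% |
|---|---|---|---|---|---|---|
| Two groups against two | 0.500 | 0.80 | 0.200 | 26.5% | 39.8% | 73 |
| One group against three equal groups | 0.433 | 0.92 | 0.173 | 20.5% | 30.5% | 97 |
| Equally spaced | 0.373 | 1.07 | 0.149 | 16.1% | 23.2% | 130 |
| Two extremes, others midway | 0.354 | 1.13 | 0.141 | 14.8% | 21.2% | 144 |

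The second row covers placebo against three equally effective active types. The N = 116 column is a ceiling: it assumes that all of the roughly 116 randomized supply endpoint data.

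**3. Two-group illustrations at d = 0.4 in change.** Two-sided t tests give 22.4% for one active against placebo (19 v 19) and 32.0% for pooled actives against placebo (57 v 19). Section 12.0 specifies no such test for CAPS-5, so these only show the scale.

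**4. Does baseline adjustment rescue it?** The ranges below run over the four patterns.

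- *0.4 in SDs of change, baseline-adjusted.* The effective f is f × √(2 / (1 + ρ)). Power is 26–50% at ρ = 0, 21–39% at ρ = 0.3, 19–35% at ρ = 0.5 and 16–29% at ρ = 0.8.
- *0.4 in SDs of the raw score, baseline-adjusted.* The effective f is f / √(1 − ρ²). Power is 19–35% at ρ = 0.5, 26–49% at ρ = 0.7 and 36–65% at ρ = 0.8. Power of 82% is reached only at ρ = 0.865 (two against two), 0.901 (one against three) or 0.935 (two extremes).
- *0.4 in SDs of the raw score, unadjusted change.* The effective f is f / √(2(1 − ρ)). Power of 82% is reached only at ρ = 0.874, 0.905 or 0.937 for the same three patterns.

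**The case against.** The strongest reply is that nothing was miscalculated: 82% is the correct power for f = 0.40, and the fault is a missing metric and a mismatched adjective. That is true as far as it goes. But the sentence as printed promises 82% power for a small-to-medium difference, and the figure applies to a difference at least twice as large. The error is in what is claimed, whatever its origin.

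Second, the 15–26% is conditional. It assumes that 0.4 is a standardized mean difference in change and that change is analysed without baseline adjustment. The cited meta-analysis is not at hand, so its metric is unverified, and the term ANCOVA in Section 12.0 leaves the form of the model open. This stands as a caution on the exact range. The direction is unaffected: an adjusted analysis of the same difference gives about 16–39% at correlations of 0.3 to 0.8, and at most 50% at zero.

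Third, this is a self-described pilot, meant partly to supply variance estimates for later trials, and its remark about pilots and power is general rather than an admission about this trial. So the remark is not a strict contradiction of the 82%, and the pilot wording does soften how a null result would be read. It does not correct a definite figure that Section 4.2 relies on.

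**Conclusion.** The concern holds. The stated 82% is right only for Cohen's f = 0.40 on change in CAPS-5, or its interaction equivalent with an assumed correlation of 0.5. That corresponds to a largest group difference of 0.80 to 1.13 SD, or 0.92 SD if the three active types are equal and differ from placebo. For a standardized mean difference of 0.4 in change, omnibus power at alpha 0.05 with 19 completers per group is 14.8% to 26.5%. Read as raw-score SDs, 0.4 reaches 82% only with a baseline-to-endpoint correlation of about 0.87 or higher, which the protocol does not state. No reading examined allows both the small-to-medium label and the 82%, short of such a correlation. Which metric the authors meant cannot be settled from the protocol, and the conclusion does not depend on it.

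**What to change.** Rewrite the power statement in Section 12.1 so that it names the metric, the test and any assumed correlation. Suggested text, if the change-score reading was intended:

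*Nineteen completers per group give 82% power (alpha 0.05) for Cohen's f = 0.40 in the four-group comparison of change in CAPS-5 total score. This is a largest between-group difference of 0.8 to 1.1 SD of change, or 0.92 SD if the three active types are equal. For a standardized mean difference of 0.4 in change, power of the same unadjusted test is about 15–26%.*

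If the interaction route, a baseline-adjusted model or a raw-score effect was intended, state the correlation assumed and give the corresponding figures. In every case, remove the small-to-medium label from beside the 82%, remove the phrase about ensuring an adequately powered size, and delete or correct the sentence extending the calculation to secondary analyses. The reference to sufficient power in Section 4.2 should then point to the corrected statement.

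The cost is protocol wording and a less favourable stated figure. No participants are added, and the endpoint and analysis stay as they are.

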3.2 Secondary Objectives

The following secondary objectives will be used to support the results of the primary objective:

1. Assess independent effects of three active concentrations of marijuana and placebo in reducing self-reported symptoms of PTSD with the PCL-5, anxiety and depression with the IDAS, and improving psychosocial functioning with the IPF and WBR (self-report and observer) among veterans during Stage 1.
2. Assess independent effects of three active concentrations of marijuana and placebo in reducing self-reported symptoms of PTSD with PCL-5, anxiety and depression with IDAS, and improving psychosocial functioning with the IPF and WBR (self-report and observer) among veterans during Stage 2.
3. Assess comparative efficacy between placebo and each active dose of marijuana based on a within-subjects analysis of PTSD symptoms as measured by the CAPS-5 in crossover participants at Baseline, End of Stage 1, Stage 2 Baseline, and End of Stage 2.
4. Assess whether Stage 2 crossover participants' preferences for marijuana concentrations in Stage 1 and Stage 2 correlate with reduction in PTSD symptoms as measured by the CAPS-5 total score.
5. Assess whether participants experience a clinically significant increase in PTSD symptoms based on CAPS-5 and PCL-5 total scores during the washout period between Stage 1 and Stage 2 compared with measures assessed at Baseline and during Stage 1.
6. Explore correlation of treatment outcomes measured by CAPS-5 score with objective changes in sleep via Actigraphy throughout the study and self-reported

- changes in sleep quality using the ISI on a weekly basis.
7. Explore correlation of Daily Diary items related to sleep with objective changes in sleep via Actigraphy and self-reported changes in sleep quality using the ISI on a weekly basis.
 8. Explore correlation of treatment effects measured by CAPS-5 total score with amount of marijuana used based on Daily Diary across Stage 1 and Stage 2.
 9. Explore treatment outcomes measured by CAPS-5 total score by marijuana concentration, with concomitant substance and medication use as a covariate throughout the treatment period.
 10. Explore durability of treatment outcomes measured by CAPS-5 total score, with any PTSD treatments based on the LTFU questionnaire treated as a covariate, six months after completing Stage 2.

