4.0 Protocol Design

This Phase 2 randomized, placebo-controlled, triple-blind, crossover, multi-site study will assess the safety and efficacy of four types of smoked marijuana to manage chronic, treatment-resistant PTSD symptoms among 76 veterans in an outpatient setting. The study will consist of a baseline period and three distinct study stages, which are described in detail below.

An initial 2-week screening period will be conducted to determine study eligibility prior to randomization, to obtain baseline measures of PTSD and substance use, to conduct study training, and ensure participants are willing and able to attend scheduled appointments and complete the study procedures.

Following randomization, participants will complete Stage 1, a three-week period of *ad-libitum* marijuana self-administration followed by a two-week period of marijuana abstinence (Cessation 1). This will be immediately followed by Stage 2, another three-week period of marijuana self-administration and two-week period of abstinence (Cessation 2). Stage 1 and Stage 2 will consist of identical procedures and measures, but the marijuana available to individual participants will vary.

During Stage 1, participants will be randomized to receive High THC, High CBD, THC/CBD, or Placebo marijuana to self-administer (up to 1.8 g/day) for the 3-week marijuana use period. As described in Section 4.2, randomization will be balanced across drug conditions (N=19 per marijuana type; total N=76). During Stage 2, the Placebo marijuana condition will be removed and all participants will be re-randomized to receive a different type of marijuana than they were assigned in Stage 1. Thus, Stage 2 will permit a within-subjects comparison of changes in CAPS-5 total score as a function of marijuana concentration, including differences in preferences for a specific marijuana concentration by self-report, and the removal of placebo as a possibility ensures that all study participants receive active marijuana at some point during the study.

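### Section 12.1 extends its four-arm power calculation to all secondary analyses, but it does not fit the within-subject placebo comparison of Secondary Objective 3, which has about 9-10 pairs for two products and none for the third

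*Protocol*

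**What the plan says.** Protocol Section 12.1 contains one power calculation. Its effect size is described as follows: "possible effect sizes are estimated to be 0.4 (small to medium effect) for a between-subject comparison". The result is that N = 76 "with 19 participants randomized to each group will have 82% power to detect these or greater differences between groups", on change in CAPS-5 total score. The section closes with "Similar calculations would apply for secondary analyses" and gives no other effect size, sample size or power. Section 12.0 sets the level: "Statistical significance ($p < .05$) will be determined for all tests".

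Section 3.2, item 3, is a different kind of comparison: "Assess comparative efficacy between placebo and each active dose of marijuana based on a within-subjects analysis of PTSD symptoms", using CAPS-5 in crossover participants at the start and end of both stages.

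Three statements decide who can contribute to it:
- Section 4.0: "During Stage 2, the Placebo marijuana condition will be removed".
- Section 4.2 re-randomizes each participant "to one of two new treatment assignments in a 1:1 ratio". It stops enrolment once 76 people have completed Stage 1, with 19 as the minimum per arm.
- Table 4 (Section 6.2.1) lists High THC and High CBD as the Stage 2 products for the placebo arm and leaves the THC/CBD cell empty. Table 6 expects 25, 25 and 26 people on the three products in Stage 2.

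**The concern.** The closing sentence of Section 12.1 follows directly on the 82% and has no limit, so it reads as covering all ten secondary objectives. Secondary Objective 3 shares neither the test, nor the sample size, nor the variance of that calculation. It is a within-person contrast, and it can draw only on people who had placebo in Stage 1 and an active product in Stage 2, which is one arm of four divided again.

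Two things are at stake. A null within-subject result could be read against a power of about 80% that this comparison probably does not have. And the objective promises a placebo comparison for every active product, while the allocation in Table 4 leaves one product with no one to compare.

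**Working it through.** **1. The plan's own figure.** The metric of the 0.4 is not named. Read as Cohen's f in a one-way four-group F test at alpha 0.05: λ = f² × N = 0.16 × 76 = 12.16, with 3 and 72 degrees of freedom. Power is 82.3%, so the stated 82% reproduces. Read as a standardized mean difference of 0.4 between two arms of 19 (two-sided t test), power is about 22%, which does not. The 82% is therefore a four-group between-subject omnibus figure.

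**2. Pairs available for Secondary Objective 3.** Start from 19 placebo-arm completers, before any loss in Cessation 1 or Stage 2.
- Section 4.2 with Table 4: 19 / 2 = 9.5 for High THC, 9.5 for High CBD, 0 for THC/CBD.
- Table 4 applied to all four arms of 19: High THC 3 × 9.5 = 28.5, High CBD 28.5, THC/CBD 2 × 9.5 = 19. This is not the 25/25/26 of Table 6.
- Totals near Table 6 arise if the placebo arm is split three ways: 9.5 + 9.5 + 19/3 = 25.3 per product. That gives about 6 placebo pairs for each product.

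**3. Illustrative power.** Paired t test, two-sided 0.05, noncentral t with n − 1 degrees of freedom and noncentrality dz × √n, where dz = d / √(2(1 − ρ)). Here d is the placebo-to-active difference in SDs of change, and ρ is the within-person correlation of the two changes. The protocol gives neither, so both are assumed. I use d = 0.4 (the stated number taken as a mean difference) and d = 0.8 (= 2f, the two-group equivalent of f = 0.40).

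| d | ρ | dz | n = 6 | n = 9 | n = 10 |
|---|---|---|---|---|---|
| 0.4 | 0 | 0.283 | 8.8% | 11.7% | 12.6% |
| 0.4 | 0.5 | 0.400 | 12.7% | 18.5% | 20.5% |
| 0.4 | 0.8 | 0.632 | 24.4% | 38.6% | 43.1% |
| 0.8 | 0 | 0.566 | 20.5% | 32.2% | 35.9% |
| 0.8 | 0.5 | 0.800 | 35.6% | 55.9% | 61.6% |
| 0.8 | 0.7 | 1.033 | 53.2% | 77.4% | 82.7% |
| 0.8 | 0.8 | 1.265 | 69.9% | 91.2% | 94.4% |

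Pairs needed per product for 82% power: 54 at dz = 0.40, 28 at 0.566, 15 at 0.80.

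If f = 0.40 arises because placebo alone differs from three equal active arms, then d = 4f/√3 = 1.6/1.732 = 0.92. Power at n = 9-10 is then 41-45% (ρ = 0), 68-74% (ρ = 0.5), 77-83% (ρ = 0.6) and 88-92% (ρ = 0.7). At d = 0.4, even ρ = 0.9 gives only 65-71%.

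**4. Stage 2 between-group test.** Three equal groups, f = 0.40. N = 76: λ = 12.16, 2 and 73 degrees of freedom, power 87.4%. The protocol gives no Stage 2 loss rate. If the loss from 116 randomized to 76 completers were repeated (76/116 = 0.655; 0.655 × 76 ≈ 50), then λ = 0.16 × 50 = 8 and power is 68.8%.

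**The case against.** The sentence speaks of similar calculations and does not literally give every secondary analysis 82%. For Secondary Objective 1 (PCL-5, IDAS, IPF and WBR in Stage 1) the design is the same four arms of 19, so it is reasonable there. This stands, and it is why the sentence should be narrowed and not deleted.

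A reader might infer that Objective 3 has at most about 62% power. The documents do not support a ceiling: the correlation is not stated, and d = 0.8 with ρ of 0.7-0.8 gives 77-94%. A reader might also infer 9-10 pairs for every product; Table 4 gives that for two products only. Nor can one conclude that the Stage 2 three-arm comparison is badly underpowered: at the 76 people that Table 6 plans it has 87%, and the 69% rests on a borrowed loss rate.

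The protocol does not prescribe a paired t test, and a mixed model over all crossover participants could borrow between-subject information. That is fair, but the objective asks for a within-subjects analysis, and no model creates placebo pairs for a product that no placebo participant goes on to receive. Nineteen is also a minimum, so counts could be somewhat higher; losses after Stage 1 work the other way.

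Finally, Section 12.1 calls the study a pilot and says that pilots are often not powered for the effect of interest. This lowers the stakes. It does not cancel the explicit extension to secondary analyses that ends the same section.

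**Conclusion.** The sentence is wrong as written, because it is unrestricted. The four-arm calculation carries over to the Stage 1 between-group secondary outcomes and not to Secondary Objective 3.

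What rests on the documents alone is the structure: one arm of at least 19 supplies all placebo pairs. Section 4.2 and Table 4 leave about 9-10 each for High THC and High CBD and none for THC/CBD, so that contrast cannot be made within subjects as the tables stand. Table 6 points to a different split.

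The size of the power shortfall rests on assumptions. With 9-10 pairs and correlations of 0 to 0.5, power is 12-21% at d = 0.4 and 32-62% at d = 0.8. Around 80% is reached with a large effect combined with a high correlation: about 0.7 at d = 0.8, or a little over 0.6 at d = 0.92. At d = 0.4 the correlation would have to exceed 0.9. The protocol supports none of these combinations. The Stage 2 between-group analysis should not be described as unpowered.

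**What to change.** In Section 12.1:
- Restrict the closing sentence to Stage 1 between-group secondary outcomes with 19 per arm.
- State that Secondary Objective 3 is not powered. Give the number of placebo-to-active pairs per product, with any power range labelled as assumed (effect size, correlation, no Stage 2 loss). Report the results as estimates with confidence intervals.
- For the Stage 2 between-group comparison, state power at the expected Stage 2 sample size: 87% at 76 for f = 0.40, lower with losses.

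In Section 6.2.1, reconcile Tables 4 and 6 with each other and with Section 4.2. Then word Secondary Objective 3 to cover only the products for which the reconciled allocation yields placebo pairs.

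The cost is a few sentences and one table check. Enrolment does not change; the stated power for one objective becomes less favourable.
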